6.2 IMPORTANT PROTOCOL DEVIATIONS

No per protocol set analysis will be performed for this study; however, the following list in [Table 6.2: 1](#) defines the different categories of potentially important protocol deviations (iPD), and it shows whether subjects will potentially be excluded from evaluations performed in this trial. The proportion of subjects with potential iPDs will be presented for completeness purposes and to demonstrate the adherence to the CTP.

Table 6.2: 1 Handling of iPDs

iPD code	iPD Category & Brief Description	Excluded from which analysis set
A	In/Exclusion Criteria not met	
A1	Inclusion Criteria not met	
A1.1	SARS-CoV-2-RNA negative (SARS-CoV-2-uninfected subjects)/positive (SARS-CoV-2-infected subjects) naso- or oropharyngeal swab obtained within 3 calendar days before study drug administration by NAAT	None
A1.2	SARS-CoV-2-infected subjects only: Onset of COVID-19 symptoms not within 7 days prior to study drug administration or No non-reactivity of serum or plasma antibodies against SARS-CoV-2 by serological assay at screening	None
A2	Exclusion Criteria not met	
A2.1	Subjects with laboratory values that indicate additional risk	None
A2.2	Patient with other underlying diseases, conditions or risks which are excluded as per clinical trial protocol	None
A2.3	Forbidden previous therapy as per clinical trial protocol	None
B	Informed Consent	
B1	Informed consent not available/not done	All
B2	Informed consent too late	None
C	Trial Medication and Randomisation	
C1	Wrong dose level received compared to dose level subject was assigned (phase I) / randomised (phase IIa) to	None
C2	Medication taken that is not matching the treatment a subject was randomised to (phase IIa only)	None
E	Missing data	

E1	No negative pregnancy test result prior to / and the end of study participation	None
E2	Missing diary data for 7 consecutive days within the first 14 days	None
F	Study Procedure Timing	
F1	Time window violation for drug administration (drug administration \leq 3 days after screening)	None
F2	Time window violation for procedures performed post baseline within the first 7 days (day 1 and day 2 without time window; day 4 within +/- 1 day; day 8 +/- 2 days)	None
G	Other Trial Specific Important Violation	
G1	Other protocol violations affecting patient rights or safety (manual PVs to be captured)	None

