### **4.3. Selection of Trial Population**

This trial is the first-in-human trial of the inhaled application as well as of the combined inhaled and intravenous application of DZIF-10c. DZIF-10c has potential use both in healthy individuals (prevention of SARS-CoV-2-infection by passive immunization) and SARS-CoV-2-infected individuals (treatment). Adults of both potential target groups will be included in this trial.

Participation in the cohort of SARS-CoV-2-infected individuals for this first-in-human trial will be restricted to adults aged 18-70 with mild-to-moderate infection not requiring supplemental oxygen at baseline (based on the inclusion criterion of the WHO Clinical Progression Scale, see **Appendix I**) as well as probable early infection (based on the duration of symptoms and/or absence of antibodies against SARS-CoV-2). In these individuals, current guidelines do not recommend the use of approved antiviral drugs. In addition, the exclusion of elderly individuals (>70 years) or individuals with significant co-morbidities will result in the enrolment of SARS-CoV-2-infected individuals at a relatively low risk of clinical progression into this first-in-human study that will focus the on safety and tolerability of DZIF-10c.

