### Groups 2A-2D

- Age 18-70.
- SARS-CoV-2-RNA positive in naso- or oropharyngeal swab obtained within 3 calendar days before study drug administration by NAAT (e.g., qRT-PCR).
- Onset of COVID-19 symptoms (e.g., sore throat, cough, fever, chills, fatigue, dys- or anosmia, dys- or ageusia, headache, muscle pain, gastrointestinal symptoms) within 7 days prior to study drug administration
  - or
  - Non-reactivity of serum or plasma antibodies (IgG; and IgA and/or IgM when tested) against SARS-CoV-2 by serological assay at screening.
- Disease severity 1-4 as defined by the WHO Clinical Progression Scale (WHO, Lancet Inf Dis 2020).

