## 5.5. Trial Drug Adminstration Visit

Prior to the study drug administration, trial staff will

- Review the informed consent form
- Discuss the planned procedure and any potential questions with the participant
- Review the interim medical history including concomitant medication
- Review screening laboratory results including safety laboratory parameters
- Review eligibility criteria
- Perform a symptom-directed physical exam
- Perform procedures and obtain samples as outlined in the Visit Schedule (**Appendix II**)
- Obtain a baseline PK serum sample
- Perform baseline assessments of vital signs
- Perform the randomization procedure (**Group 2D only**)

- Perform a pulmonary function test (**Groups 1A-1C** only)

If the screening visit of healthy volunteers (**Groups 1A-1C**) occurred >3 calendar days prior to the start of the antibody administration, the negative NAAT result of an additional naso- or oropharyngeal swab obtained within (inclusive) 3 calendar days of the antibody inhalation must be available prior to the start of the drug administration (e.g., rapid PCR from swab obtained on the day of inhalation).

DZIF-10c or placebo will be prepared by the local pharmacy and administered as described in Section 5.9.

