Appendix II B - Visit Schedule - Groups 2A-2D - **SARS-CoV-2-INFECTED PARTICIPANTS**

Version: V04\_0 01-APR-2021

Visit	1	2	3	4	5	6	7	8	9	10	11
Study Week	Screen 	Wk 0				Wk 1		Wk 2	Wk 4	Wk 8	Wk 13
Study Day	D-3 to D 0	D 0	D 1	D 3	D5 	D 7	D10 	D 14	D 28	D 56	D 90
Visit Window (+/- days)	-	-	-	1	1	1	1	2	3	4	7
Eligibility and History											
Informed Consent	x										
Inclusion/Exclusion criteria	x										
Demographics/Medical History	x										
Medical History	x	x	x	x	x	x	x	x	x	x	x
Concomitant Medication	x	x	x	x	x	x	x	x	x	x	x
Study Intervention											
Randomization		(x) 									
In-Patient Admission		(x) 									
Study Drug Administration	x										
Study Procedure											
ECG	x										
Inhalation-related Events (+ Infusion-related in Group 2D )	x	x	x	x	x						
Adverse Events		x	x	x	x	x	x	x	x	x	x
General Physical	x										
Directed Physical 	x	x	x	x	x	x	x	x	x	x	x
Vital Signs 	x	x 	x	x	x	x	x	x	x	x	x
Weight	x								x		x
Height	x										
Pregnancy counseling	x										
Pregnancy testing in women of childbearing potential	x	x 						x	x	x	x
WHO R&D Clinical Progression Scale	x	x	x	x	x	x	x	x	x	x	x
Biosamples											
Virology screening labs  (Local lab)	x										
Safety lab  (Local lab)	x	x	x	x		x		x	x	x	x
Coagulation parameters (INR, PTT) (Local lab)	x										
SARS-CoV-2 antibody serology (Local lab)	x	x									
Urinalysis  (Local lab) ( Groups 2A-2C only )	x					x		x			x
PK samples (Central lab)	x 	x	x	x	x	x	x	x	x	x	x
Nasopharyngeal SARS-CoV-2 swab (Central lab)	x	x	x	x	x	x	x	x	x	x	x
Oropharyngeal SARS-CoV-2 swab (Central lab)	x	x	x	x	x	x	x	x	x	x	x
Naso- or Oropharyngeal SARS-CoV-2 swab (Local lab)	x 										
Oropharyngeal SARS-CoV-2 swab (Local lab)		(x  )									
Anti-DZIF-10c antibody (ADA) assay sample (Central lab)	x							x	x	x	x
Research lab (PBMCs) (Central lab)		x							x		x

1. In **Group 2D**, screening and infusion procedure may be performed on the same day. SARS-CoV-2 swabs for central lab PCR are mandatory to be obtained prior to the infusion.
2. Trial visits on day 5 and day 10 are considered optional pending local capacity for quarantine visits.
3. Randomization in **Group 2D** only.
4. In-patient admission required in **Groups 2A-2C**, and at the discretion of the investigator in **Group 2D**.

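### Three rules in the SAP's important-protocol-deviation table (A1.2, F1, F2) do not match the protocol; only the reported proportion of deviations is affected

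*SAP*

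**What the plan says.** **A1.2.** Protocol 4.3.1 gives Groups 2A-2D two alternative routes to show early infection. One is symptom onset "within 7 days prior to study drug administration"; the alternative to it is "Non-reactivity of serum or plasma antibodies (IgG; and IgA and/or IgM when tested) against SARS-CoV-2 by serological assay at screening". Protocol 4.3 describes the same restriction as "based on the duration of symptoms and/or absence of antibodies against SARS-CoV-2", so one route is enough. SAP Table 6.2: 1 lists the matching deviation in two parts joined by or: the first part is "Onset of COVID-19 symptoms not within 7 days prior to study drug administration", and the second part is "No non-reactivity of serum or plasma antibodies against SARS-CoV-2 by serological assay at screening".

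**F1.** The code is labelled a time-window violation for drug administration. Its parenthesis gives dosing at most 3 days after screening, with no distinction by group. The protocol's screening windows are D-7 to D-1 for Groups 1A-1C (Appendix II A) and D-3 to D 0 for Groups 2A-2D (Appendix II B). Protocol 5.5 provides for healthy volunteers screened more than 3 calendar days before dosing: in that case "the negative NAAT result of an additional naso- or oropharyngeal swab obtained within (inclusive) 3 calendar days of the antibody inhalation must be available" beforehand.

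**F2.** The code's windows are "day 1 and day 2 without time window; day 4 within +/- 1 day; day 8 +/- 2 days". Both visit schedules give the protocol day 7 visit a window of 1 day either side. SAP 4.2 raises every day label by 1, so protocol day 7 is SAP day 8.

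**Use of the table.** SAP 6.2 presents the proportion of participants with potential important deviations for completeness and to show adherence to the protocol. There is no per-protocol analysis, and A1.2, F1 and F2 each have None in the exclusion column.

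**The concern.** A deviation rule should be true exactly when the protocol requirement is broken. The opposite of an either/or criterion is that both halves fail. A1.2 instead fires when either half fails, so it puts participants who were properly enrolled in the same count as those who were not. F1 can count healthy volunteers who kept to their own screening window, while F2 passes over visits that fell outside theirs. The errors run in both directions and do not cancel in any useful way. What is at stake is the accuracy of a figure that the trial report will offer as evidence of adherence, including adherence to the early-infection restriction in the infected groups.

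**Working it through.** The plan gives no figure to reproduce. The check sets each rule beside the protocol requirement.

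**A1.2.** Let A = onset within 7 days and B = non-reactive serology. The protocol requires A or B, so the violation is (not A) and (not B). A1.2 as written is (not A) or (not B).

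| A | B | Eligible under protocol 4.3.1 | Flagged by A1.2 as written | Flagged if both halves must fail |
|---|---|---|---|---|
| yes | yes | yes | no | no |
| yes | no | yes | yes | no |
| no | yes | yes | yes | no |
| no | no | no | yes | yes |

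Three of the four combinations are eligible and three of the four are flagged; the two middle rows are flagged although eligible. The third row includes asymptomatic participants if absence of onset is programmed as onset not within 7 days. They can be enrolled: score 1 on the scale in protocol Appendix I is asymptomatic infection, and scores 1-4 are eligible.

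**F1.** Read as a limit (dosing more than 3 days after screening is a violation), it accepts lags of 0 to 3 days.
- Infected groups: the protocol allows 0 to 3 days. No difference.
- Groups 1A-1C: the protocol allows 1 to 7 days. Volunteers dosed 4, 5, 6 or 7 days after screening comply but would be flagged.
- SAP 4.2 gives 3 subjects per cohort, so at most 3 x 3 = 9 healthy volunteers could be involved. The documents do not say how many were dosed at those lags.

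Read literally, the parenthesis describes compliance, so the code would flag the wrong side of the limit.

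**F2**, in SAP day labels (protocol day + 1):

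| Protocol visit | Protocol window | F2 window | Out of window but not counted |
|---|---|---|---|
| D 1 | 2 | 2 | none |
| D 3 | 3-5 | 3-5 | none |
| D 5 (optional) | 5-7 | not listed | not checked |
| D 7 | 7-9 | 6-10 | 6 and 10 |

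The relabelling moves the centre of a window by 1 and leaves its width alone. The remark in SAP 4.3 about deliberate differences from the flow charts refers to the study day, so it does not account for the wider limit.

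**The case against.** The best defence is that the table was never meant as program logic. Its column holds brief descriptions, and A1.2 sits under a heading saying that inclusion criteria were not met. Neighbouring entries are equally loose: A1.1 describes a compliant swab without negating it, F1's parenthesis describes compliance, and the A2 heading says that exclusion criteria were not met. On that view a participant who satisfies the either/or criterion is never a deviator, whatever A1.2 says. The table also covers potentially important deviations, so 2 days at day 8 could be a chosen threshold of importance.

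Part of this stands. Over-flagging under A1.2 follows only if the line is programmed literally, and the documents do not show that it was. But A1.2, unlike A1.1, is written out in negated form, and the negation is wrong. The SAP nowhere says that F2's wider limit is intended.

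A reader might infer four stronger things, none of which the documents support:

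- **That the report could not show whether the early-infection restriction was respected.** SAP 5.4.1.2 lists days since symptom onset and antibody status, SAP 7.1 tabulates them, and SAP 6.4 adds subgroup summaries on both. These are summaries of each half, not of the combination, but they do not depend on A1.2.
- **That treatment estimates are affected.** The three codes exclude nobody.
- **That F2 loosens the 7-day analyses.** The primary endpoint counts adverse events by onset within 7 days of dosing (SAP 5.1, 7.4.1). The 7-day viral-load analysis stops 7 days after dosing and has its own substitution rule, day 7 for a missing day 8 (SAP 6.7, 7.5.2.2.3). A swab on SAP day 10 is outside it whatever F2 says. A swab on SAP day 6 may simply be the optional protocol day 5 visit.
- **That a definite number of eligible participants will be listed as deviators.** The mix of onset and serology is not given. As an illustration only, take the two halves as independent with probabilities p and q. The flagged share of eligible participants is then 1 - pq/(p + q - pq). With p = 0.95 and q = 0.90 it is 1 - 0.855/0.995 = 14%, about 8 of the 60 in Group 2D. With p = 0.70 and q = 0.50 it is 1 - 0.35/0.85 = 59%, about 35 of 60. Neither input has a source in the documents, and the width of the range shows that no figure can be claimed.

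**Conclusion.** The mismatch holds for all three codes. A1.2 is logically wrong as worded. F1 does not fit the healthy-volunteer screening window and is ambiguously phrased, though its 3-day limit agrees with the protocol for infected participants. F2 is wider than the protocol at one post-dose visit and agrees at days 2 and 4. Applied as written, A1.2 and F1 would overstate deviations and F2 would understate them. The consequence is a potentially inaccurate descriptive proportion and nothing beyond it. This rests on the codes being programmed as worded (for F1, as a 3-day limit) and on no importance threshold for F2 being documented elsewhere. The severity is minor.

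**What to change.** In SAP Table 6.2: 1:

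- **A1.2:** flag only when onset is not within 7 days (or there are no symptoms) and serology is reactive at screening.
- **F1:** word it as the violation and make it group-specific, using the protocol screening windows (D-7 to D-1 for Groups 1A-1C, D-3 to D 0 for Groups 2A-2D). No swab-timing clause is needed, because A1.1 already covers the 3-day swab requirement.
- **F2:** set day 8 to 1 day either side, as in Appendix II A and B, or state that the wider limit is a deliberate threshold of importance.

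The cost is three table lines and the matching program logic. No new data are needed and no other analysis has to be rerun.

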6.3 SUBJECT SETS ANALYSED

- Screened set (SCS):
 - This subject set includes all subjects having signed informed consent and would correspond to the intention-to-treat set (ITT) in the phase I part of the trial.
- Randomised set (RS):
 - This subject set includes all randomised subjects in the phase IIa part of the trial, whether treated or not. This would correspond to the intention-to-treat set (ITT) in the phase IIa part of the trial
- Treated set (TS):
 - This subject set includes all subjects who received any amount of study drug.
- Modified Treated set (mTS):
 - This subject set includes all subjects who received any amount of study drug and did not require replacement in the phase I part of the trial. Details about requirement for replacement can be found below.
- Modified Intention-To-Treat set (mITT):
 - This subject set includes all randomised subjects in the phase IIa part of the trial that received any amount of study drug and who have at least a baseline value and a second measurement in the first week (up to 7 days after drug intake) of viral RNA shedding in nasopharyngeal swabs by qRT-PCR.

- PK parameter analysis set (PKS):
 - This subject set includes those subjects in the TS with at least one valid serum concentration of DZIF-10c available

Participants who are withdrawn from the trial after DZIF-10c administration will not be replaced, except for participants during the dose-escalation phase of the trial that are not followed until at least the day 7 visit after drug administration for reasons not related to safety events. Subjects who were replaced will be excluded from the primary analysis of the primary endpoint. Replacement of subjects will be determined on a case-by-case basis; exclusion of these subjects from the primary analysis will be confirmed by the trial team at the report planning meeting prior to database lock.

Please see [Table 6.3: 1](#) for a general overview which patient set will be used for which type of analyses. Additionally, biomarker analyses might be performed on subsets of the mITT set.

Table 6.3: 1 Subject sets used in the different types of analysis

Type of analysis	Subject set					
	SCS	RS	TS	mTS	mITT	PKS
Primary endpoints			X		X ^[1]	
Further endpoints				X		
Safety data, ADA & treatment exposure				X		
Demographic/baseline characteristics				X		
Disposition		X	X			
PK parameters						X
Viral Load				X ^{[1][2]}	X	

^[1] Will be used for the phase I part of the trial.

^[2] Will be used for analyses of OP swabs.

Note that the number of subjects with available data for an endpoint may differ. For details, see [Section 6.6](#).

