### **5.2.3. Assessment of Viral Shedding**

#### SARS-CoV-2 RNA assessment

SARS-CoV-2 RNA levels will be determined from frozen (-80°C) transport medium using a clinically validated quantitative reverse-transcripase real-time PCR assay (qRT-PCR) assay. Results will be provided as Ct (Cycle threshold) values as well as quantitatively (copies/ml) based on a reference standard. These assays will be performed at the Institute of Virology at the University Hospital Cologne.

At the screening visit, a single naso- and/or oropharyngeal swab is sufficient to document the absence or presence of SARS-CoV-2 infection by qRT-PCR. This assay is performed at the trial site's local laboratory. In any case, in SARS-CoV-2-infected individuals, both nasopharyngeal and oropharyngeal swabs must be obtained for the central laboratory prior to study drug administration.

To provide participants with early results about the presence or absence of SARS-CoV-2 in swab samples prior to the determination of results at the central laboratory, an additional oropharyngeal swab may be obtained and sent for NAAT (e.g., qRT-PCR) at the local routine laboratory. This optional additional swab is to be obtained after the oropharyngeal swab for central laboratory evaluation.

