#### Screening Visit

At the screening visit, the Principal Investigator or subinvestigator will explain and discuss the aims and nature of the trial, potential risks, and the trial schedule with potential participants who will be provided the opportunity to address all questions and concerns they may have with study staff, relatives, and friends. Prior to the initiation of any study-related procedures, written informed consent will be obtained from each participant.

If the potential participant provides informed consent to participate in this trial, study staff will

- Obtain a complete medical history including the use of concomitant medication (including medication within the last 4 weeks prior to screening)
- Perform a general physical exam, including height, weight, vital signs (heart rate, blood pressure, body temperature, respiratory rate, and pulse oximetry), and examination of the skin and respiratory, cardiovascular, abdominal, and neurological systems
- Provide pregnancy counseling
- Determine the clinical score based on the WHO Clinical Progression Scale (**Groups 2A-2D**)

- Perform a pulmonary function test (**Groups 1A-1C**)
- Collect blood, urine, and swab samples for all tests indicated in the Visit Schedule (**Appendix II**)
  - At the screening visit, a single nasopharyngeal and/or oropharyngeal swab may be obtained to document absence or presence of SARS-CoV-2 infection. This swab is to be analyzed at the trial site's routine laboratory. An available SARS-CoV-2-RNA NAAT result documented in writing from a sample obtained within three days prior to trial drug administration is considered as an acceptable alternative. In all cases, nasopharyngeal and oropharyngeal swabs must be obtained at baseline prior to study drug administration in SARS-CoV-2-infected individuals.

Screening and Trial Drug Administration Visit Procedures may occur on the same day during the expansion phase of the trial (**Group 2D**).

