5. ENDPOINTS

In this section, more details are given regarding endpoints. Note that for all endpoints and analyses, [Section 6.7](#) should be consulted for baseline value definition. Analyses for the first interim analysis will be based on all data collected until the data snapshot for interim database lock 1 (iDBL1). Analyses for the second interim analysis will be based on all data collected until the data snapshot for iDBL2. Analyses for the final CTR reported after the final DBL will be based on all data collected within the trial. Information on the interim database locks and corresponding analyses can be found in [Section 9.1](#) of this TSAP.

Handling of missing data points is described in [Section 6.6](#).

For endpoints where the “date of last contact” is utilised, the following will apply:

- The last contact date when the subject was known to be alive is defined as the latest date recorded in the electronic Case Report Form (eCRF) from the dates listed below (in case a date is planned to be imputed for the analysis, the imputed date will also be used for the definition of “date of last contact”):
 - Date of last visit, data of last reported Adverse Event (AE) (excluding censored dates and end dates when outcome is fatal or unknown), date of last reported concomitant treatment, date of last laboratory sample, date of drug intake, last contact date (as documented on the end of study eCRF page if the reason for not completing the planned observation period is NOT “Death”), vital status date (from the end of study if the subject is known to be alive) and the latest of vital status date / last successful contact date (from the vital status eCRF page if the subject was lost to follow-up).

For endpoints where viral load is utilised, the following will apply:

- Viral load measurements below the limit of valid quantification (2116 copies/mL for the E gene and 1950 copies/mL for the ORF1a/b gene) will be set to half this limit on the log10 scale (46 and 44.16 copies/mL, respectively). This imputation will also be applied for negative swab test results.

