In addition to a time-weighted average change, changes from baseline will also be evaluated using a restricted maximum likelihood (REML) based repeated measures approach. Analyses will include the fixed, categorical effects of antibody status, and treatment-by-visit interaction, as well as the continuous, fixed covariates of baseline and baseline-by-visit interaction. An unstructured (co)variance structure will be used to model the within-subject measurements. In

case the model does not converge, other covariance structures will be used sequentially until convergences is reached and the used covariance structure will be reported. The sequence of covariance structures to be used is as follows: unstructured, antedependence, heterogeneous Toeplitz, Toeplitz, heterogeneous AR(1). The Kenward-Roger approximation will be used to estimate denominator degrees of freedom.

All model-based evaluations (time-weighted average change and MMRM) will be done for the following time periods:

- first 7 days after drug administration
- first 14 days after drug administration
- first 28 days after drug administration

Note that only data points within the analysis periods are considered. Data available after the cut-offs will not be considered for the model based evaluations.

All model-based evaluation will be done for the SARS-CoV-2 E gene. As sensitivity analyses, the evaluations will be repeated for the additionally assessed SARS-CoV-2 gene (ORF1a/b gene). This sensitivity analysis will be done on subjects from the subject set TS who have at least a baseline value and a second measurement in the respective time period of viral RNA shedding in OP swabs by qRT-PCR.

Clearance rate

It will be shown how many patients fell below the limit of valid quantification. Finally, the proportions of participants with positive and negative PCR for each assessed SARS-CoV-2 gene assessed at every given visit will be described (clearance rate). Missing data will not be imputed. Consequently, the number of patients with non-missing data will be used as denominator for each proportion. CIs for the proportions will be derived as Clopper-Pearson intervals.

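### Group 2D participants who are NP-negative before dosing enter the viral-load set and the clearance denominator: clearance is inflated, difference-scale contrasts shrink, and the ratio of means is exposed to chance imbalance

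*SAP*

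**What the plan says.** **Entry.** Protocol 4.3.1 (Groups 2A-2D) requires a "SARS-CoV-2-RNA positive in naso- or oropharyngeal swab obtained within 3 calendar days before study drug administration by NAAT". Protocol 5.2.3 says of the screening swab: "This assay is performed at the trial site's local laboratory". Protocol 5.4 also accepts the following in its place: "An available SARS-CoV-2-RNA NAAT result documented in writing from a sample obtained within three days prior to trial drug administration". The endpoint baseline is a different sample, the central-laboratory NP swab taken before dosing. No section requires that swab to be positive.

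**Analysis set.** The mITT (SAP 6.3) consists of randomised, treated participants "who have at least a baseline value and a second measurement in the first week (up to 7 days after drug intake"). Protocol 8.1.1 is no stricter on this point. For periods beyond 7 days, SAP 7.5.2.2.3 uses treated participants with a baseline and a second value, which leaves the same opening.

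**Value of a negative swab.** SAP 5 sets results below the limits of valid quantification ("2116 copies/mL for the E gene and 1950 copies/mL for the ORF1a/b gene") to half the limit on the log10 scale, and adds: "This imputation will also be applied for negative swab test results".

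**Clearance rate.** SAP 7.5.2.2.3 states that "the proportions of participants with positive and negative PCR for each assessed SARS-CoV-2 gene assessed at every given visit will be described (clearance rate"), and that "the number of patients with non-missing data will be used as denominator for each proportion".

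**The concern.** A participant can qualify on a throat swab, or on a sample up to three days old, and be negative on the central NP swab that supplies the baseline. That baseline then sits at the imputed floor, so the change from baseline can be zero or upward but never downward. If the participant stays negative, the record adds zeros to the change analyses and a cleared result to every visit, with no NP virus at baseline to clear.

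The Protocol (8.1.4) calls the time-weighted change in viral RNA its main efficacy analysis, and SAP 9.1.2.1 uses viral-load change at the second interim analysis to inform later development. Arms have 20 participants and randomisation is unstratified (Protocol 5.9.4), so a few such participants, or an uneven split of them, can change what is read from the results.

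**Working it through.** **1. The plan's own figures.** Half the limit on the log10 scale: 0.5 × log10(2116) = 1.663, and 10^1.663 = 46.00 copies/mL. For ORF1a/b, 0.5 × log10(1950) = 1.645, which gives 44.16. Both match SAP 5. A negative baseline is therefore 1.663 log10 (E gene), and no later value can be lower.

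**2. Input the documents do not give.** The share f of participants NP-negative at baseline is unknown; 5% to 30% is assumed. At f = 5% the chance of at least one among 60 is 1 − 0.95^60 = 95%. At f = 10% it is 1 − 0.90^60 = 99.8%.

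**3. Difference scale.** Suppose negatives stay negative and f is equal in both arms. Each arm mean is then (1 − f) times the mean in baseline-positives, and so is the difference. Take an assumed placebo TWA change of −1.5 log10 and a ratio of 1.45, the figure in Protocol 8.2 borrowed for illustration. The active mean is −2.175 and the true difference −0.675.

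| f | (1 − f) × (−0.675) | Simulated ANCOVA with baseline covariate |
|---|---|---|
| 10% | −0.607 | −0.610 |
| 20% | −0.540 | −0.538 |
| 30% | −0.472 | −0.471 |

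The simulation used 4,000 trials per row with a baseline mean of 6.5 log10. The linear baseline covariate does not restore the difference. Restricting to baseline-positives returns about −0.66 to −0.67 at every f.

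**4. Ratio scale.** The TWA contrast in SAP 7.5.2.2.3 is a ratio of adjusted means. With equal f the factor cancels: (1 − f)μ₁ / (1 − f)μ₀ = μ₁/μ₀. In the same simulation the median ratio is 1.45 at every f.

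Chance imbalance does not cancel. A second simulation assumed baseline 6.5 log10 (SD 1.3), decline of 0.45 versus 0.65 log10/day, between-person slope SD 0.15, measurement SD 0.4, swabs at 0, 1, 3, 5 and 7 days after dosing, values below the limit set to 1.663, and ANCOVA on baseline.

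- Balanced negatives (0, 10 or 20%): ratio about 1.40 throughout.
- 1 negative on placebo, 4 on active: about 1.34. Reversed: about 1.48.
- No drug effect, 1 versus 4: a spurious adjusted difference of about 0.09 log10.

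Without adjustment the 1-versus-4 split would give 1.40 × (16/20)/(19/20) = 1.18, or 1.40 × (19/20)/(16/20) = 1.66 reversed. The covariate therefore removes most of this bias, but not all of it.

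**5. Clearance rate.** With k negatives of 20 and true clearance p among baseline-positives, the reported rate is (k + (20 − k)p)/20.

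- p = 30%: k = 2 gives (2 + 5.4)/20 = 37%; k = 4 gives (4 + 4.8)/20 = 44%.
- Equal true rates of 40%, with k = 1 versus 4: (1 + 7.6)/20 = 43% against (4 + 6.4)/20 = 52%.
- True rates of 20% and 40%: the 20-point gap becomes 28% against 46% (18 points) at f = 10%, and 36% against 52% (16 points) at f = 20%.

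**6. Precision.** In the second simulation, excluding negatives raises the mean |estimate/SE| from 2.56 to 2.94 (f = 10%) and from 2.35 to 2.79 (f = 20%). With slope SD 0.25 the gain is smaller, 1.97 to 2.07 and 1.84 to 1.96. In the model of step 3, nominal ANCOVA power hardly changes: 0.58 with negatives against 0.57 without at f = 10%, and 0.52 against 0.51 at f = 20%. Any gain depends on the assumed between-person variability.

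Antibody status, the other planned covariate, was left out of both simulations, and negatives were held at the floor throughout.

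**The case against.** The strongest reply has four parts.

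- **The planned TWA contrast is a ratio, so balanced negatives do not dilute it.** This is correct. Shrinkage in proportion to f applies to MMRM differences, to arm-level adjusted means and to clearance differences. What remains for the ratio is chance imbalance.
- **A negative NP swab does not make a participant unable to respond.** Group 2 is selected for probable early infection (Protocol 4.3), so NP positivity may follow, and limiting that rise would be an antiviral effect. This also stands. The calculations hold these participants at zero change, which is an assumption, and excluding them discards whatever they would show.
- **The plan already shows much of this.** Baseline CT values and copies/mL are tabulated (SAP 5.4.1.5), PCR-positive and -negative proportions are given by visit, and baseline viral load is a covariate. These displays let a reader infer the baseline-negative share, but they do not correct the clearance denominator or the shrunken differences. The baseline subgroup in SAP 6.4 splits at 10^6 copies/mL, which pools negatives with low positives.
- **The trial is exploratory, the clearance rate is descriptive, and the mITT follows the Protocol.** This argues against replacing the main analysis set. It does not argue against a correctly labelled proportion or a sensitivity analysis.

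The clearance paragraph names no analysis set of its own, so that part of the point rests on its stated denominator.

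**Conclusion.** The gap is real and follows from the rules as written: a baseline-negative participant enters the mITT and is counted in the clearance rate. The clearance rate is inflated (a true 30% reads 37% or 44% with 2 or 4 negatives of 20). Difference-scale contrasts shrink by about the share of negatives if they stay negative. The TWA ratio is unaffected when negatives are balanced and moves to about 1.34 or 1.48 instead of 1.40 under a 1-versus-4 split. All sizes rest on an assumed share of negatives and assumed viral kinetics, since the documents give neither.

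A reader might infer that the trial's main antiviral estimate is diluted in general, that these participants cannot respond whatever the drug does, and that dropping them reliably gains precision. The documents do not support this. The planned TWA contrast is a ratio, a later rise to NP positivity is possible, and the precision gain varies with the assumed variability. The point warrants a cheap addition to the SAP, not a new main analysis set.

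**What to change.** 1. Keep the protocol-defined mITT as the main set for the 7-day viral-load analyses.
2. In SAP 7.5.2.2.3, compute the clearance rate among participants PCR-positive on the central pre-dose swab of the same type and gene.
3. Pre-specify a sensitivity analysis of the TWA change and the MMRM restricted to participants with a positive central pre-dose swab.
4. Report the number baseline-negative per arm, by swab type and gene.

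The flag uses a sample taken before dosing, so the restricted comparison remains one between randomised arms. The cost is SAP wording and one derived variable from data already collected. The restricted analyses lose a few participants, have a slightly larger SE in some settings (0.228 to 0.247 at 20% negative with slope SD 0.15), and carry no information from those who turn positive after baseline. Keeping the mITT as the main set retains that information.
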